The general study enrollment and investigational plan for Year # 1 (2020) and Year # 2 (2021) is illustrated and outlined in Figure 1 and Figure 2 respectively. Details regarding each individual study visit are illustrated and outlined in Figures 3-7. The study visits and details regarding each visit are further detailed in section 10 “Study Visits”.

The study PI and other investigators will be blinded to the allocation of participants to either carnosine or placebo. The participants will also be blinded to their allocation. The Randomization Committee (RC) will be in possession of the randomization key so that accurate unblinding of the randomization assignment may be identified in the event of a medical or other Carnosine NEAT Trial Protocol
Version Date 5-14-2020

emergency. The RC will consist of four individuals: the pharmacist compounding the supplement ([name]), the study physician ([name]), a member of the UofL Clinical Trials Unit, and the study biostatistician ([name]). Study supplements (carnosine or placebo) will be prepackaged into punch cards and marked with letters "A" or "B". The contents of series "A" or "B" will be part of the blinded randomization and will be known only to the RC. The study supplements will be directly shipped, stored and handled by the UofL CTU.

An initial screening (Visit # 1) of potential / interested participants will be conducted to identify eligible candidates based on eligibility criteria established *a priori*. Eligible candidates will be invited to a complete baseline assessment (Visit # 2). Randomization and allocation will occur between Visit # 1 and Visit # 2. Participants invited for Visit # 2 will already be randomized into one of the two study groups (carnosine or placebo). Participants from both study groups will be followed up at 6 weeks (Visit # 3) and 12 weeks (Visit # 4). Relevant and extensive data for primary and secondary endpoints will be collected at Visit # 2 through Visit # 4. The data collected throughout all visits (# 1 through # 4) may be used to generate preliminary data for future studies.

Visit # 1 will focus on consenting the participant for the entire study, collect contact/demographic information, and collect a urine sample. Safety assessments will be conducted at Visit # 3 and Visit # 4. Participants may be contacted for up to 12 months after enrollment via phone/email/mail for safety, adverse events, and or general follow up questions.

Study Endpoints

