Blinding of the study personnel recruiting the participants and giving the pill-boxes will be facilitated by the fact that all study participants (Carnosine and placebo) will receive a dietary supplement. All study dietary supplements will be matched in color, consistency, and taste. The primary and secondary endpoints of the study will be determined by core laboratories whose personnel are blinded to supplementation assignment. In addition, the study recruitment and regulatory teams will take steps to ensure that endpoint and adverse event assessments are carried out in a blinded fashion.

Should unblinding occur, the Executive Committee consisting of the study PI, the study physician, and UofL CTU will be informed about the circumstances and they will discuss the circumstances related to the unblinding and further course of action. Any instance of unblinding will be documented in the study database and will be reported to the IRB as required.

Study Supplement Requirements

Study Supplement Packaging and Labeling

Study supplement packaging and labeling will meet all local and federal requirements. Study supplement (carnosine and placebo) label includes the product number, letter "A" or "B", volume, expiration date and time, storage conditions, and contact name and address. All supplements will be labeled for investigational use only.

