Supplement capsules will be pre-sorted into monthly (28 day) pill boxes by the unblinded laboratory personnel at the University of Colorado, Skaggs School of Pharmacy and Pharmaceutical Sciences. Pre-sorted pill boxes will be created for a total of 12 weeks per participant. The University of Colorado, Skaggs School of Pharmacy and Pharmaceutical Sciences personnel will label each box clearly as letter "A" or letter "B", indicating whether the box contains Carnosine or placebo supplement. The study personnel at the University of Louisville involved in recruitment, processing, analysis, or any other direct participant contact will be blinded to whether "A" boxes contain Carnosine or placebo, and similarly whether "B" boxes contain Carnosine or placebo. The University of Colorado, Skaggs School of Pharmacy and Pharmaceutical Sciences personnel will ensure that there is absolute consistency in the contents of each series of labeled boxes. The University of Colorado Skaggs School of Pharmacy and Pharmaceutical Sciences will ensure that the contents of each box are not disclosed to anyone involved with the study (staff, investigator, or participant) and will directly and securely send the randomization key to the Randomization Committee (study physician and UofL CTU).

Study Supplement Storage Requirements

L-Carnosine is tested on arrival to establish its purity and retested about every 6-12 months. L-Carnosine receives a three-year dating each time it passes re-assay. Product is stored at controlled room temperature. A sample of packed capsules will be retained, which will be re-assayed about every six months. Potency and stability testing services will be provided using Nuclear Magnetic Resonance and Liquid Chromatography/Mass Spectrometry in the Medicinal Chemistry Core Facility of the University of Colorado, Skaggs School of Pharmacy and Pharmaceutical Sciences.

United States Pharmacopeia (USP) <795> allows 180 day dating for compounded capsules, with extension of dating with ongoing stability studies. Initial potency and purity are established using Nuclear Magnetic Resonance and Liquid Chromatography/Mass

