15. STATISTICAL PROCEDURES

Randomization

Randomization to Carnosine assignment will be conducted using a statistical software by one of the study statisticians. The randomization key detailing which participant is in which group (Carnosine or placebo) will be maintained by the Randomization Committee (RC) consisting of the study physician ([name]) and a member of the UofL CTU. After the investigator or research coordinator verifies that screening testing is complete and the inclusion and exclusion criteria for the study have been satisfied, an un-blinded member of the Randomization Committee will have secured access to the participant's supplement assignment.

Participants will be randomized to the Carnosine or placebo group, using a block size of 6. The stratification factors are sex, age (two group) and carnosine level (two group). When a participant is identified from the screening process (data from Visit # 1), the clinical recruitment team will be informed whether the participant will be receiving supplements from pill-box labeled "A" or "B. The clinical recruitment team will assign the participant a study ID from a pre-defined series, which will have no bearings on supplement randomization process.

As detailed in Section 11 "Study Supplement", the University of Colorado Skaggs School of Pharmacy and Pharmaceutical Sciences will ship 28-day pill-boxes (total 3 per participant) pre-filled with either Carnosine or placebo. These boxes will also be pre-labeled with large sized visible letters "A" or "B". The entire study team, excluding the Randomization Committee, will be blinded to whether "A" or "B" series contains Carnosine versus placebo. The University of Colorado, Skaggs School of Pharmacy and Pharmaceutical Sciences personnel will ensure that there is absolute consistency in the contents of each series of labeled boxes. The University of Colorado Skaggs School of Pharmacy and Pharmaceutical Sciences will directly and securely transmit the randomization key and other relevant information to the Randomization Committee (study physician and UofL CTU).

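### All supplement boxes carry one of two fixed letters known to staff and participants, so if one box's content reaches anyone holding the letters, every arm under that key can be deduced

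*Combined protocol and SAP*

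**What the plan says.** **Two codes, fixed content.** Section 15 (Randomization) says of the pill-boxes: "These boxes will also be pre-labeled with large sized visible letters", A or B. Section 11 (Study Supplement Packaging and Labeling) says the pharmacy's "personnel will label each box clearly as letter" A or B, and that it "will ensure that there is absolute consistency in the contents of each series of labeled boxes". Section 15 repeats the requirement. Section 8 (Study Design) describes punch cards rather than boxes, but with the same two letters.

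**Who sees the letter.** Once a participant is identified from screening, "the clinical recruitment team will be informed whether the participant will be receiving supplements from pill-box labeled" A or B (Section 15). The letter is also on the product itself: "Study supplement (carnosine and placebo) label includes the product number, letter" A or B (Section 11). Participants take the boxes home. Sections 11 and 15 blind staff to what the letters mean, not to which letter a participant has.

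**What happens on unblinding.** Section 8 gives the Randomization Committee the key so that "accurate unblinding of the randomization assignment may be identified in the event of a medical or other" emergency. Section 11 (Randomization and Blinding) says the Executive Committee, made up of the principal investigator, the study physician and the Clinical Trials Unit, is informed of the circumstances, and that "they will discuss the circumstances related to the unblinding and further course of action". Whether the arm itself is disclosed is not stated. Section 8 requires the principal investigator to be blinded.

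No participant-specific code, scrambled code, yearly re-keying or limit on the spread of a code break is described. The label has a product number, but nothing says it is unique to a participant, and it stands beside the letter.

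**The concern.** A double-blind trial with an emergency unblinding procedure should be able to break one code without weakening the others. Here all participants share two codes, so the secret is a single binary fact. It concerns people already allocated, so varying the block size would not protect it.

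There are two ways in which that fact could reach people who hold the letters.

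- **Formal unblinding.** The case goes to a committee that includes the principal investigator, and no rule withholds the arm.
- **Inference.** Sections 10 and 16 list effects such as tingling and stomach upset, and side effects are discussed with each participant at Visits 3 and 4. Two letters let staff pool those reports over everyone seen so far. With unique codes there is nothing to pool.

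At stake are the measures that depend on people rather than on an assay:

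- arterial stiffness, a secondary endpoint, which a research team member runs (Section 12);
- adverse-event causality, which the principal investigator chooses (Section 13), and grading, which matters because Grade 1 events are not entered in the electronic case report form;
- the handgrip test, in which the assessor gives verbal feedback (Appendix E), and the interview-style questionnaires (Section 8);
- adherence and retention, in a trial that expects 40% attrition.

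**Working it through.** **Inputs from the documents**

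- Evaluable participants: 240; attrition: 40%; randomized: 400 (Section 8). Section 11 gives two hundred per arm.
- Distinct codes: 2, with "absolute consistency in the contents of each series of labeled boxes" (Section 15).
- Enrolment planned in two equal yearly cohorts (Executive Summary).

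**Input assumed.** The chance *p* that a given participant is unblinded. The documents give no figure, so a range of 0.05% to 1% is used.

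**Step 1. Reproduce the number sharing the codes.** 240 / (1 − 0.40) = 240 / 0.60 = 400, which matches the plan.

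**Step 2. Count the arms deducible after one break.** With two letters and two fixed contents, knowing the content of one letter fixes the other. Someone who holds the letters can then deduce:

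- scheme as written: 400 of 400 (100%);
- letters re-keyed each year (not stated): 400 / 2 = 200 of 400 (50%);
- participant-specific codes: 1 of 400 = 0.25%.

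These counts do not depend on *p*. They do require that the decoded content reach someone with the letters. An outside clinician without the letter list would learn one participant's arm only.

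**Step 3. Chance of at least one unblinding.** With independent participants this is 1 − (1 − *p*)^N.

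| Assumed *p* | N = 400 | N = 200 (one year) |
|---|---|---|
| 0.05% | 18% | 10% |
| 0.1% | 33% | 18% |
| 0.5% | 87% | 63% |
| 1% | 98% | 87% |

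For example, at *p* = 0.5%: 1 − 0.995^400 = 0.865.

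**Step 4. What the table does not give.** It is the chance that any unblinding occurs. If each unblinding leaks the letter's meaning to someone holding the letters with probability *q*, the chance of a leak is 1 − (1 − *pq*)^N, which cannot exceed the tabulated value. The documents give no basis for *q*. The inference route is additional and cannot be quantified either, since no side-effect rates by arm are given.

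**The case against.** **That one emergency unblinding by itself reveals everyone.** A reader might infer this, but the documents do not say it. Unblinding runs through the Randomization Committee, which already holds the key. The Executive Committee learns the circumstances; disclosure of the arm is not stated. Two of its three components, the study physician and the Clinical Trials Unit, are already among the key holders, so only the principal investigator could be newly informed by that route. This stands: the exposure is conditional on the content reaching someone who has the letters. What remains is that nothing in the plan prevents this.

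**That an unblinding is close to certain.** The upper rows of the table might suggest it. Section 14 expects too few serious events to support formal stopping rules, and Section 16 reports no complications in earlier similar trials in healthy participants. The participant's identification card already states both possible capsule contents. All of this favours the low end, although 18% at the lowest assumed rate is not negligible.

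**That the primary result is compromised.** The documents do not support this. Endothelial progenitor cells, microparticles and platelet-monocyte aggregates are laboratory measures, and Section 11 has core-laboratory personnel blinded to assignment. Stored-sample labels, as listed in Section 8, do not include the letter. An indirect route through retention or adherence remains, unquantified. The core-laboratory statement does not settle arterial stiffness, which is acquired at the visit.

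**That blinding could not be recovered for the second year.** The 2021 cohort could be re-lettered. The plan does not say so, and one break would still expose about 200.

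**That the people told the letters are the assessors.** Section 15 refers to the clinical recruitment team and Section 12 to a research team member. Overlap is plausible but not stated, and Section 11 commits to blinded endpoint and adverse-event assessment. Section 9 also refers to a Manual of Operations that is not among the documents.

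**Conclusion.** The concern holds in conditional form. The coding scheme makes the blind of up to 400 participants depend on one fact, and the plan has no safeguard if that fact reaches anyone who holds the letters. Participant-specific codes would reduce the exposure from one break to 1 of 400.

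The 400 and the 1 follow from the scheme as described, provided letters are not re-keyed; yearly re-keying would make it about 200. The 18% to 98% chance of at least one unblinding rests wholly on assumed rates, with the documents pointing to the low end, and bounds the formal route only from above.

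The reach is mainly to arterial stiffness, adverse-event grading and causality, physical function tests, questionnaires, and adherence or retention. The physical function tests and questionnaires are not listed endpoints. No stated calculation changes, and the laboratory readings are protected. This is a cheap improvement that should be made, not a defect that undermines the primary comparison.

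**What to change.** Replace the letters with one unique kit number per participant, shared by that participant's three 28-day boxes and scrambled so that it carries no information about the arm.

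- **Section 8, Study Design:** replace the A/B marking with the kit number. Reconcile who holds the key: four people here, but only the study physician and a Clinical Trials Unit member in Sections 11 and 15.
- **Section 11, Randomization and Blinding:** state that the principal investigator is told that an unblinding occurred but not the arm, and that only the one kit is decoded.
- **Section 11, Packaging and Labeling:** print the kit number instead of the letter, and confirm that the product number does not differ by arm. The kit-to-content list is held only by the pharmacy and the unblinded key holders.
- **Section 11, Accountability:** check kit numbers on receipt instead of the letter.
- **Section 15, Randomization:** tell the recruitment team the kit number only.

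**Cost.** New labels and a kit list from the pharmacy that already packs and labels each box. The Clinical Trials Unit must match kit numbers at dispensing rather than choose between two series. Allocation, sample size and analysis are unchanged.

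**Limit.** Kit numbers do not blind the study physician, who holds the key and also assesses the relatedness of events (Section 14). That overlap needs its own resolution.

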5. EXECUTIVE SUMMARY

[figure not shown]
Study Design: This is a randomized, double-blind, placebo-controlled longitudinal clinical intervention study to assess the physiologic effects of dietary supplementation of carnosine in healthy human participants. Carnosine is a naturally synthesized peptide in the human body, and is also commercially available as a dietary supplement. The primary endpoint in this study are endothelial progenitor cells (EPCs) found in peripheral blood. Exposure to PM_{2.5} is known to decrease levels of EPCs, which represent angiogenesis.

EPCs will be compared between carnosine and placebo groups at 6 weeks and also their change from baseline to 6 weeks to 12 weeks post initiation of intervention. The secondary endpoints are difference in EPCs at 12 weeks between carnosine versus placebo groups and difference in arterial stiffness, endothelial microparticles, and platelet monocyte aggregates between carnosine versus placebo groups at 6 weeks and 12 weeks.

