6. STUDY OBJECTIVES

Primary Objective

The primary purpose of this study is to determine whether taking carnosine as a dietary supplement protects the vasculature from PM_{2.5} air pollution-induced oxidative stress in healthy human subjects. The primary endpoint is difference in EPCs between Carnosine versus placebo groups at 6 weeks and 12 weeks.

Secondary Objective

The secondary objective of this study is to determine whether taking carnosine as a dietary supplement is protective from PM_{2.5} air pollution-induced arterial dysfunction, endothelial damage, and pathological platelet activation in healthy human subjects. The secondary endpoints are difference in arterial stiffness, endothelial microparticles, and platelet monocyte aggregates between Carnosine versus placebo groups at 6 weeks and 12 weeks.

Hypothesis (for Primary and Secondary Objectives)

Carnosine supplementation blunts adverse effects of PM_{2.5} pollution on vasculature of healthy participants.

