Primary Endpoints (reflecting change from baseline to 6 weeks and 12 weeks and between groups)

1. Difference in EPC-2 between Carnosine and Placebo Groups
2. Difference in EPC-3 between Carnosine and Placebo Groups
3. Difference in EPC-4 between Carnosine and Placebo Groups
4. Difference in EPC-7 between Carnosine and Placebo Groups
5. Difference in EPC-8 between Carnosine and Placebo Groups

Secondary Endpoints (reflecting change from baseline to 6 weeks and 12 weeks and between groups)

1. Difference in Arterial Stiffness between Carnosine and Placebo Groups
2. Difference in Endothelial Microparticles between Carnosine and Placebo Groups
3. Difference in Platelet Monocyte Aggregates between Carnosine and Placebo Groups

Data Collection Tools

Blood Samples

A sample of ~3 table spoons (~45 ml) of blood will be obtained by venipuncture performed by a study staff trained in phlebotomy using standard procedures and precautions to insure the safety of the participants and phlebotomist. If any subject becomes ill, uncomfortable, or desires to withdraw, he/she may do so at any time. Blood sample collection protocol is detailed in Appendix A. Samples will be promptly transported to the Diabetes and Obesity Center's research laboratory on the 4th floor of the Delia Baxter building ([name]) for processing, storage, and analysis. After processing, samples will be aliquoted in appropriately labeled vials and stored in (-80C) freezer. Stored samples will contain study name, participant ID, date of sample acquisition, type of sample, and visit type. Samples will be stored in de-identified fashion and participant personal information or PHI will not be displayed/barcoded on any stored sample. Samples will be stored for future use, ancillary studies, and or preliminary data development.

The measurement of blood biomarkers for primary and secondary endpoints from blood samples (EPCs, microparticles, and PMA) are further detailed in Appendix B.

Urine Samples

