There are 5 primary endpoints: difference in EPCs (EPC-2, EPC-3, EPC-4, EPC-7, and EPC-8) between Carnosine and placebo groups at 6 weeks and 12 weeks. These endpoints will be evaluated at the alpha=0.01. There are four secondary endpoints: difference in EPCs between Carnosine and placebo groups at 12 weeks, difference in EPCs between Carnosine and placebo groups at 6 weeks, difference in arterial stiffness between carnosine and placebo groups at 6 and 12 weeks, difference in endothelial microparticles between carnosine and placebo groups at 6 and 12 weeks, and difference in platelet monocyte aggregates between carnosine and placebo groups at 6 and 12 weeks.

Continuous variables will be presented by summary statistics (such as mean, median, standard error, range, 95% CI, correlations) and the categorical variables by frequency distributions (frequency counts, percentages and 95% CI). We will also calculate correlations along with confidence intervals. To identify significant differences due to intervention, we will compare the differences using a two sample t-test. We will use regression (logistic or linear) to model and test the effect of other covariates such as age and race. We also will compare outcome measures using GLM and MIXED model procedures to account of repeat observations. General statistical analyses will be performed with the SAS statistical software package (SAS Institute Inc., Cary, NC).

Statistical Monitoring Rule

[figure not shown]
Safety monitoring of the accumulated outcomes data is designed to ensure the continuing safety of the currently enrolled participants and participants not yet enrolled. This is achieved by stopping the trial early to reduce the number of participants exposed to a harmful or ineffective supplementation.

Monitoring Non-efficacious Supplementation (Futility)

We do not plan any interim analyses for futility due to longer follow-up (1 year).

Monitoring Toxic Supplementation (Safety)

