The cumulative number of grade 3 or 4 toxic events will be monitored after each person is enrolled ⁴⁸. If the cumulative number of toxic events produces enough evidence to conclude that the true toxicity rate is greater than or equal to 33% ($Pt_0 = 0.33$) then the trial will be stopped early for safety reasons. If the cumulative number of toxic events after person is treated is greater than or equal to the associated boundary value b_i then the combination supplementation is rejected for safety considerations (monitoring table with these boundaries will be generated using Ray and Rai, 2011)⁴⁸. With this rule, there is only a 5% chance of stopping the trial early for lack of safety if the true toxicity rate is less than 33%. Continual assessment of the toxic events ensures we do not expose an undue number of participants to a harmful supplementation.

A second sub-analysis to be executed is the effect of Carnosine supplementation in participants with cardiovascular disease compared to the effect of Carnosine supplementation in participants without any cardiovascular disease.

Subgroup Evaluations

The effect of subgroup stratum on the relationship between carnosine supplementation and the endpoints (both primary and secondary) will be assessed. If a carnosine supplementation effect is demonstrated, it is not likely to behave identically among all important subgroups. The subgroups of interest are age, sex, race, socioeconomic status, diabetes, smoking, hypertension, and cardiovascular disease risk scores.

These additional analyses can sometimes be helpful in identifying extreme differences in the effects of supplementation among subgroups, although the literature wisely warrants that caution be used in interpreting subgroup analyses.

Additional Analyses

We will use the 6 week and 12-week EPC levels to assess the change of EPCs from baseline to 6 weeks and 12 weeks, assessing if this trajectory is related to carnosine supplementation using mixed model analysis of variance.

We will evaluate the relationship among the indices of the primary endpoint – EPCs. Specifically, we will assess the relationship between the differences in EPCs, adjusting for important baseline covariates.

[figure not shown]
Multiple Comparisons

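### The five primary EPC comparisons rest on an unadjusted two-sample t-test, with no specified adjustment for baseline EPC or the sex and carnosine strata

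*Combined protocol and SAP*

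**What the plan says.** Section 15, Primary and Secondary Endpoints, states how a treatment effect will be identified: "To identify significant differences due to intervention, we will compare the differences using a two sample t-test". Section 8, Sample Size Computations, bases 120 per arm on a two-sample t-test at alpha 0.01.

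Two other methods follow in the same paragraph of Section 15, with no ranking:
- A repeated-measures analysis, with no model terms given: "We also will compare outcome measures using GLM and MIXED model procedures to account of repeat observations"
- A covariate regression, with two example covariates: "We will use regression (logistic or linear) to model and test the effect of other covariates such as age and race"

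Under Additional Analyses, Section 15 plans a further look at EPC change over time, "assessing if this trajectory is related to carnosine supplementation using mixed model analysis of variance". It also plans an analysis among the EPC indices themselves: "Specifically, we will assess the relationship between the differences in EPCs, adjusting for important baseline covariates".

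The outcome variable is worded in different ways. Section 8 heads its list "Primary Endpoints (reflecting change from baseline to 6 weeks and 12 weeks and between groups"; Section 6 says "The primary endpoint is difference in EPCs between Carnosine versus placebo groups at 6 weeks and 12 weeks"; Section 5 says "EPCs will be compared between carnosine and placebo groups at 6 weeks and also their change from baseline". Section 15 also lists the EPC differences at 6 weeks and at 12 weeks among the secondary endpoints.

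Randomisation is stratified by sex, two age groups and two carnosine levels (Sections 8 and 15).

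**The concern.** The t-test is the implied primary analysis: it is the method linked to the intervention effect, and the trial is sized on it. It uses neither the stratification factors nor baseline EPC as a covariate. None of the alternatives clearly fills the gap. The regression sentence gives age and race as examples and speaks of testing covariates, not treatment. The GLM/MIXED sentence gives no model terms. The mixed model under Additional Analyses names no covariates. The one reference to baseline covariates concerns relations among EPC indices, and the subgroup section concerns effect modification.

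Two things are at stake. The first is precision: a change score gives baseline a fixed weight of one, which is too much when the correlation between visits is moderate. The second is pre-specification: with several unranked methods, the result that decides each endpoint stays open until the data are seen.

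**Working it through.** **Inputs (Section 8).** 120 per arm; alpha 0.01 (sidedness not stated); power 0.90; effect 0.5 SD; correlation 0.5 between consecutive visits, with 0.80 as a second value in the table; pilot SD of EPC-2 0.702561.

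**Reproducing the plan's figure.** At correlation ρ the change score has variance 2(1−ρ) in units of SD², which is 1.00 at ρ = 0.5. Two-sided, n per arm = 2 × (2.576 + 1.282)² × 1.00 / 0.5² = 119.04, so 120. One-sided alpha gives 105, so two-sided is used below. The noncentral-t power with 120 per arm is 89.8%.

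**Which variable is tested.** With 120 per arm at ρ = 0.80, a change-score t-test gives these detectable effects for EPC-2, -3, -4, -7 and -8:
- 80% power: 0.1974, 0.0030, 0.0159, 0.1159, 0.1943. The printed 80%/0.80 row is 0.197, 0.003, 0.016, 0.116, 0.194.
- 90% power: 0.2228, 0.0034, 0.0180, 0.1308, 0.2193. The row printed as 90%/0.50 is 0.223, 0.003, 0.018, 0.131, 0.219.

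For EPC-2 at 80% power, a follow-up-only t-test gives 0.312 and ANCOVA at ρ = 0.80 gives 0.187, so neither fits the 80%/0.80 row. The other two rows do not match a change-score test as labelled: 80%/0.50 prints 0.351 against 0.312, and 90%/0.80 prints 0.156 against 0.223. As printed, 90% power also has a smaller detectable effect than 80% at the same correlation, which cannot be. The table therefore supports the change-score reading but does not prove it.

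**Variance at one visit** (equal variances, linear relation, baseline EPC as the only covariate). Follow-up only: 1. Change score: 2(1−ρ). Baseline-adjusted: 1−ρ². Cut against the change score: 1 − (1+ρ)/2.

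| ρ | Follow-up only | Change | Adjusted | Cut v change | Power at 0.5 SD, change v adjusted |
|---|---|---|---|---|---|
| 0.5 | 1.00 | 1.00 | 0.75 | 25% | 89.8% v 96.9% |
| 0.8 | 1.00 | 0.40 | 0.36 | 10% | 99.98% v 99.99% |
| 0.25 (assumed) | 1.00 | 1.50 | 0.94 | 37.5% | 71.4% v 91.9% |

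A simulation with 120 per arm and 8,000 runs gave cuts of 25.2% at 0.5 and 9.4% at 0.8. The effect detectable with 90% power falls from 0.50 to 0.43 SD at ρ = 0.5 and from 0.317 to 0.301 SD at 0.8. By noncentral t, 90% power at ρ = 0.5 needs 121 per arm with the change score and 91 with adjustment. At ρ = 0.5 a follow-up-only test has the same variance as the change score, so the 25% does not depend on which reading is right. At 0.8 the cut against follow-up only is 64%.

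**Fewer completers** (assumption, 100 per arm, ρ = 0.5): 82.4% v 93.0%.

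**Average of both visits** (assumption, all correlations 0.5). Change: (1+0.5)/2 + 1 − (0.5+0.5) = 0.75. Adjusted: 0.75 − 0.5² = 0.50. The cut is 33%, and power is 96.9% v 99.8%.

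**Skew.** The pilot SD exceeds the mean for four of the five EPCs (not EPC-3). Simulations from the EPC-2 and EPC-7 pilot mean and SD (raw correlation 0.5, mean shift 0.5 SD, 4,000 runs per cell) compared the change-score t-test with raw-scale ANCOVA:
- Normal: 89 to 90% v 97%.
- Gamma or lognormal, additive shift: 88 to 90% v 95 to 97%.
- Gamma or lognormal, multiplicative effect: 71 to 78% v 75 to 84%.

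Under skew the gain is 4 to 7 points. Rejection under the null was 0.7% to 1.2% for both tests.

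**The case against.** The strongest reply is that the plan may not intend a single-visit test. Section 15 lists the week-6 and week-12 EPC differences as secondary, so the primary comparison may use both visits. With all correlations at 0.5, the unadjusted change score then already has about 97% power. Section 8 also calls both the 0.5 correlation and the 40% attrition conservative. The gain shrinks as correlation rises: power is 95.8% v 98.7% at 0.6 and 99.2% v 99.8% at 0.7. The larger losses come from assumptions outside the plan's stated values (100 completers, correlation 0.25). Finally, a mixed model with baseline as a response and a common baseline mean would recover about the same precision as ANCOVA.

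Most of this stands as a limit on size. It does not close the gap. The plan does not say which visit or combination is primary. It gives its correlation only for consecutive visits, so the baseline to week-12 value is unstated. Its mixed model is not specified in the form that recovers the gain: with complete data, an unconstrained arm-by-visit contrast with baseline as a response reproduces the change-score result.

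**Conclusion.** The concern holds. The implied primary test is valid under randomisation and meets the plan's own target, so this is a recommended improvement and not a correction of bias. Against a single-visit change-score t-test, adjustment for baseline EPC removes 25% of the variance at correlation 0.5 and 10% at 0.8. The benefit counts where the plan has no slack: at 0.5 its 90% power needs all 120 completers per arm. At 0.8 almost nothing is lost for a 0.5 SD effect.

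The power figures rest on normal data, equal variances and two-sided alpha 0.01; under skew only the direction of the gain is stable. Any added gain from the strata cannot be computed from the documents. The absence of a named primary method and contrast is a defect whatever the correlation.

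**What to change.** In Section 15, Primary and Secondary Endpoints, name one primary analysis for each EPC endpoint: the planned MIXED model of EPC at 6 and 12 weeks, with arm, visit, arm-by-visit, baseline EPC, sex, age group and carnosine stratum (or the matching ANCOVA for a single visit). State the one contrast tested at alpha 0.01: week 6, week 12 or their average. Keep the two-sample t-test as a sensitivity analysis. Because skew is likely, fix the analysis scale from a blinded check of pooled baseline data before unblinding.

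The cost is plan wording and one blinded data look; baseline EPC and the strata are already collected, and no participants or visits are added. The endpoint statements in Sections 5, 6, 8 and 15 should be aligned with the chosen contrast. The Multiple Comparisons paragraph, which interprets p-values at a nominal 0.05, should be reconciled with the 0.01 level. On the raw scale the reported effect remains a difference in means. If a transformed scale is chosen, it does not, and the Section 8 detectable effects would need restating.
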